Protocol Summary

Rejuvenation of Aged Muscle Stem Cells Through Exercise

BACKGROUND AND SIGNIFICANCE: Continuous physical exercise is a potent method of preserving muscle mass with aging. In terms of muscle stem cell (referred to as satellite cells) health, exercise rescues the aging-associated loss of satellite cells and improves the ability to regenerate muscle after injury. The mechanisms for exercise-induced improvements in satellite cell function are currently unclear. However, exercise has been shown to induce AMPK activity, autophagy and decrease apoptosis in muscle. Moreover, autophagy regulates satellite cell mitochondrial function and proliferative capacity in young and old satellite cells. We have preliminary data showing an exercise-induced increase in autophagy and proliferation in aged satellite cells in the mouse. Based on these findings it is justifiable to investigate the effect of exercise training on satellite cell autophagy/apoptosis in young and aged human's populations to ensure translational capacity to our research program. We hypothesize that exercise will increase muscle stem cell function in young and older individuals through induction of cellular autophagy and survival mechanisms.

FUNDING SOURCE: [name], Ph.D. will be the Principal Investigator for this study. [name], M.D. and [name], M.D. will be the physicians and Co-Investigators on this study. The study will be funded by the National Institutes of Health/National Institute on Aging.

PURPOSE OF STUDY: The proposed study will establish a newly-identified signaling pathway regulating both autophagy and apoptosis in human satellite cells. These findings will allow for novel pharmacological targets in satellite cells to return regenerative capacity to elderly individuals.

DESIGN AND PROCEDURES: Up to 80 adults, 21 years of age and greater, will undergo a consent visit followed by three blood draws and muscle biopsy visits- baseline (pre), after the first exercise bout (post-acute), and after the 12 week training program (post-chronic). Blood will be obtained and tested for inflammatory (IL-6/TNF/IL-1) and endocrine markers (Testosterone/Estrogen/Thyroid hormone). As part of the intervention, participants will undergo moderate intensity treadmill exercise three times per week for 10-12 weeks or serve as sedentary controls. The specifics of the biopsy visits are described in the consent and have been repeated here:

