- **Visit 1:** The consent visit will take place at the Duke Center for Living and will last one hour. We will explain the study and the consent form in detail and on an individual basis.
- **Visit 2:** This 1-hour visit will take place at the Center for Living.
 - A brief medical history including list of medications will be performed.
 - A blood sample of up to 20 mL will be collected from consented participants through venipuncture.
 - A baseline muscle biopsy procedure will be performed by either [name] M.D. or [name] M.D., both of whom have extensive experience with this procedure in previous studies. The subject will be told to avoid products such as aspirin medication up to five days before this visit to reduce the risk of excess bleeding from the biopsy incision site (also avoid ibuprofen, naproxen the day before this visit). After local anesthesia (xylocaine, 2%) is injected, a small incision will be made in the left thigh. Four to six small pieces of muscle about the size of a pea will be surgically removed. The incision site will be closed using steri-strips. This part of the visit takes approximately 30 minutes. All muscle samples will be stored in a -80°F freezer at the Duke Molecular Physiology Institute.

The Exercise Training Program: After Visit 2, subjects will be randomized to one of two intervention groups. Group 1 will be required to attend 3 supervised exercise sessions per week for 10-12 weeks. They will be fitted with a heart rate monitor around the chest to maintain running intensity. Each exercise session will begin with a short warm-up before performing submaximal (70% age predicted heart rate) exercise on a treadmill or stationary bicycle for 30 minutes. Group 2 will be the sedentary control group. This group will be asked to maintain their baseline level of inactivity.

- **Visit 3:** This 1-hour visit will take place at the Center for Living. For those participants assigned to exercise intervention, this will take place approximately 2-hours after the first bout of exercise. For the control participants, this visit will occur approximately 1 week after the baseline visit.
 - This visit will follow the same procedures as Visit 2, described above.

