- Thigh Muscle biopsies may result in momentary pain and discomfort, burning or bleeding, numbness, and rarely fainting or infection. Please notify [name] or study staff if you have taken any product containing aspirin within five days of the muscle biopsy as aspirin can increase bleeding risk. The incision site may leave a scar and muscle soreness may be present up to ten days after the biopsy.
- Xylocaine: While the local numbing medicine xylocaine is almost entirely free from allergic properties (such as causing hives), an allergic reaction is possible, and the participant will not be given xylocaine if they have a history of such a reaction. The xylocaine will be given by a small injection into the skin at the site of the muscle biopsy.
- Risks associated with a standard blood draw include momentary discomfort and/or bruising. In addition, there is a minimal risk of infection, excess bleeding, clotting, and fainting.
- An exercise program may result in muscle, bone and/or joint soreness, discomfort and/or injury.

Any adverse events will be reviewed and signed off on by the PI as they occur. Adverse events will then be reported to the IRB in accordance with HRPP policies.

Participants may benefit from the exercise portions of this study through improved physical function and cardiorespiratory fitness

COST TO THE SUBJECT: The subjects will not incur any costs as a result of participation in this study. Immediate necessary care is available if an individual is injured because of participation in a research project. However, there is no provision for free medical care or for monetary compensation for such injury. During this study, hospitalizations or additional care beyond the scope of this study will be the responsibility of patients and/or their insurance company.

DATA ANALYSIS AND STATISTICAL CONSIDERATIONS: Muscle stem cell function will be compared across age groups at each time point using a One Way ANOVA or t test for specific comparisons. An alternative analysis will be a longitudinal design following muscle stem cell function from each individual before and after exercise training. This analysis will be performed with repeated measure ANOVAs. Data will

be analyzed using GraphPad Prism 6 statistical software. Significance will be accepted as $p < .05$.

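### Neither stated analysis compares the randomised exercise and control arms, so the exercise hypothesis is not tested by the randomisation

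*Protocol*

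**What the plan says.** The Background and Significance section of the protocol states the hypothesis: "We hypothesize that exercise will increase muscle stem cell function in young and older individuals". The paragraph on the exercise training programme sets the design: "After Visit 2, subjects will be randomized to one of two intervention groups". Group 1 trains under supervision three times a week for 10-12 weeks; "Group 2 will be the sedentary control group". Both arms have blood draws and biopsies at Visits 2, 3 and 4. The sample is "Up to 80 adults, 21 years of age and greater".

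The section Data Analysis and Statistical Considerations names two analyses:

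- Lead: "Muscle stem cell function will be compared across age groups at each time point using a One Way ANOVA or t test", the latter for specific comparisons.
- Alternative: a longitudinal analysis by repeated measures ANOVA, "following muscle stem cell function from each individual before and after exercise training".

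Significance is set at p < .05. Neither analysis mentions arm, Group 2 or an arm-by-time term, and no other section does so. The protocol gives no effect size, standard deviation, allocation ratio or age-group sizes.

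**The concern.** The hypothesis is about an effect of exercise, and the design randomises exercise so that its effect can be separated from everything else. The factors the analysis section compares are age group, which is not randomised, and time within a person, which has no control.

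- The age-group analysis has one factor. At Visits 3 and 4 each age group contains both exercisers and controls. A benefit shared by young and old cancels out of the age contrast, and a benefit confined to one age group is diluted by that group's controls.
- The before-after analysis credits exercise with any change over three biopsies: response to repeated biopsy, season, changed behaviour, or laboratory variation between visits. The control arm exists to remove such changes, but it is not used.

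A significant result from either analysis could not be attributed to exercise by virtue of the randomisation. Controls would undergo three biopsies, with the discomfort and scarring described in the risk section, for no stated comparison.

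**Working it through.** **What each analysis can estimate**

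| Element | Factor | Where stated |
|---|---|---|
| Hypothesis | Exercise | Background and Significance |
| Randomised factor | Exercise or control | Exercise training programme |
| Lead analysis | Age group, at each visit | Data Analysis |
| Alternative analysis | Time within individual | Data Analysis |

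The hypothesised and randomised factors agree; the analysed factors differ from them. The protocol has no figure of its own to reproduce here.

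**Inputs for the illustration.** From the protocol: at most 80 participants, alpha 0.05. Assumed: two-sided tests, two age groups, 1:1 allocation (20 per age-by-arm cell), outcome SD 1, no age difference without exercise, no dropout.

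**Age test at Visit 4.** Let exercise add δ_Y in young and δ_O in older exercisers. Half of each age group exercises, so

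expected age difference = (δ_O − δ_Y)/2.

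- δ_Y = δ_O = 0.8: the difference is 0. Simulated rejection is about 3% (3-4% across runs). This is below the nominal 5% because mixing arms inflates the within-group variance, to about 1 + 0.4² = 1.16. The arm comparison, 40 versus 40, has noncentrality 0.8 × √(40/2) = 3.58 and power of about 94%.
- δ_Y = 0, δ_O = 0.8: the difference is 0.4. The average within-group variance is about (1 + 1.16)/2 = 1.08, so noncentrality is (0.4/√1.08) × √20 = 1.72 and power is about 39-40%. An arm comparison within older participants, 20 versus 20, has noncentrality 0.8 × √(20/2) = 2.53 and power of about 69%.

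**Before-after test when exercise does nothing.** Take 40 exercisers, a drift of D outcome SDs and within-person correlation ρ. The SD of the change is √(2(1 − ρ)), so noncentrality = D × √40 / √(2(1 − ρ)). At ρ = 0.5 the SD of change is 1.

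| Drift D | Noncentrality (ρ = 0.5) | Declared significant |
|---|---|---|
| 0 | 0 | 5% |
| 0.2 | 1.26 | 23% |
| 0.3 | 1.90 | 46% |
| 0.5 | 3.16 | 87% |

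At D = 0.3 the rate is 35% for ρ = 0.3 and 67% for ρ = 0.7. In simulation at ρ = 0.5, the arm comparison of change stays at about 5% for every drift shown, because drift common to both arms cancels.

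Pooling the controls into the before-after test without an arm factor makes matters worse: with 80 people and ρ = 0.5, drifts of 0.2, 0.3 and 0.5 SD are declared significant 43%, 76% and 99% of the time.

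**What the arm comparison offers.** With 40 per arm, the difference detectable with 80% power is (1.96 + 0.84) × √(2/40) = 0.63 SD of the quantity compared.

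**The case against.** The strongest reply is that the paragraph is silent on arm and does not exclude it. A repeated measures ANOVA can carry a between-subject factor. The design section labels the visits of all participants by exercise (pre, post-acute, post-chronic), so before and after training may simply name visits and include the controls. With only young and older groups a one-way ANOVA would be unnecessary, so the author may have had age-by-arm cells in mind, or age comparisons within each arm. A separate statistical analysis plan, not available here, could supply the contrast.

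These readings are possible but not written. The t tests for specific comparisons belong to the sentence on age groups and name no arm. Including controls in the longitudinal analysis still gives no arm contrast unless arm is a factor. The protocol does more than leave the model open: it names the factors to be compared, and an analysis plan that followed it faithfully would repeat the problem.

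Some of the objection stands:

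- The percentages rest on assumed inputs, and the age-test figures also assume that arms are pooled within age group. Nothing in the protocol supports a particular amount of drift, and laboratory batch drift between visits is not established, since samples are stored frozen.
- The remedy has limits. If only older people gain 0.8 SD, a pooled arm test has about 39% power and the arm-by-age interaction about 42%. The gain comes from the within-older contrast (about 69%).

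**Conclusion.** The concern holds and must be fixed. The analysis section fixes age group and time as the factors compared, whereas the hypothesis and the randomisation concern exercise versus control. Carried out as written, it gives no randomised test of exercise. This conclusion is structural and needs none of the assumed numbers.

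The numbers show how much could be lost. Under the hypothesised pattern of equal benefit in both age groups, the lead analysis has essentially no chance of detecting an effect that the arm comparison would usually find. The alternative analysis has a false-positive rate that rises well above 5% with modest drift. Both depend on the assumed cell sizes, effect sizes, drift and correlation.

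**What to change.** Reword the Data Analysis and Statistical Considerations paragraph as follows:

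1. Primary analysis: exercise versus control in the change in muscle stem cell function from Visit 2 to Visit 4, all participants analysed as randomised.
2. One longitudinal model with arm, time, age group and their interactions. Report the arm effect with a confidence interval within young and within older participants, and the arm-by-age interaction as secondary, noting its limited power.
3. State separately the arm contrast intended at Visit 3. That visit falls about 2 hours after the first bout in exercisers and about 1 week after baseline in controls, so its interpretation should be spelled out.
4. Keep cross-sectional age comparisons for baseline or within arm, and treat the before-after test in exercisers as descriptive.

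The cost is one paragraph and a slightly larger model. The data are already planned for both arms, so no added participants, visits or biopsies are needed. Any separate statistical analysis plan should be aligned with the new wording.

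### The lead analysis compares age groups visit by visit, and no stated test uses the randomised control to estimate the exercise effect or asks whether that effect differs by age.

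*Protocol*

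**What the plan says.** The study title is "Rejuvenation of Aged Muscle Stem Cells Through Exercise". The hypothesis, under Background and Significance, is that "exercise will increase muscle stem cell function in young and older individuals". Design and Procedures gives the size: "Up to 80 adults, 21 years of age and greater, will undergo a consent visit". After the baseline biopsy at Visit 2, participants are randomised to supervised exercise or to a sedentary control group. Biopsies are repeated at Visits 3 and 4 in both groups.

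Data Analysis and Statistical Considerations sets out two analyses, with significance at 0.05:

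- Lead: "Muscle stem cell function will be compared across age groups at each time point using a One Way ANOVA or t test".
- Second: "An alternative analysis will be a longitudinal design following muscle stem cell function from each individual before and after exercise training". On method it adds only: "This analysis will be performed with repeated measure ANOVAs".

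The exercise and control groups are not mentioned in either description, and age is mentioned only in the first.

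**The concern.** A one-way ANOVA or t test across age groups at a single visit has one factor, age. It asks whether the ages differ at that visit. It does not ask whether either age group responded to exercise, or whether one responded more than the other. Any age gap at Visit 2, before randomisation, is carried into the Visit 4 comparison.

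The second analysis does look at change within a person. As worded, though, it is a before-and-after comparison. Without the control arm, a change from Visit 2 to Visit 4 mixes the exercise effect with anything else that moves the measurement over 10-12 weeks. Without age, it cannot say whether young and older participants changed by different amounts.

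Two conclusions are at stake. The written hypothesis, improvement in both ages, needs the exercise-versus-control contrast, which randomisation makes available and neither analysis uses. A claim that exercise brings aged cells closer to young ones needs a contrast of the exercise effect between ages, and none is stated.

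**Working it through.** The Protocol gives no effect size, SD, power or split by age or arm, so there is no stated figure to reproduce. The check has an algebraic part and an illustration.

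**1. What each stated analysis estimates.** Let G2 and G4 be the young-minus-old gaps at Visits 2 and 4, and let Cy and Co be the mean changes in young and old. Then

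G4 = G2 + (Cy − Co).

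The Visit 4 age test is a test of G4 = 0. If both ages respond equally, Cy − Co = 0 and G4 = G2, so the test simply repeats the baseline gap. The contrasts that bear on the study questions are:

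- exercise effect: change in exercisers minus change in controls (arm by visit);
- age difference in that effect: the exercise effect in young minus that in old (age by arm by visit; age by arm once baseline is adjusted for).

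The lead analysis contains neither. The second, as worded, supplies only change within individuals.

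**2. Illustration: reading significance visit by visit.** Assumptions, none of them in the Protocol:

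- two age groups with the same true gap d at both visits (no narrowing), d = 0.5 to 1.0 SD;
- correlation ρ between visits of 0.3 to 0.7;
- two-sided t tests at 0.05;
- either 20 per age group (exercisers only, 80 split equally into four cells) or 40 per age group (arms pooled).

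Each setting used 20,000 simulated trials. The pattern counted is p < 0.05 at Visit 2 and p ≥ 0.05 at Visit 4. Entries at single gaps are for ρ = 0.5.

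| Per age group | d = 0.5 | d = 0.65 | d = 0.8 | d = 1.0 | Range over d and ρ |
|---|---|---|---|---|---|
| 20 | 15.5% | 16.8% | 14.7% | 8.9% | 6.6-20.7% |
| 40 | 16.2% | 10.8% | 4.4% | 0.6% | 0.6-19.3% |

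Among trials with a significant Visit 2 gap at 20 per group, the gap loses significance by chance in 7.6-54.8%. A t test comparing change between ages rejects in 4.8-5.2% of trials in every setting.

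Hand check at n = 20, d = 0.8: d√(n/2) = 0.8 × √10 = 2.53, so per-visit power is about Φ(2.53 − 1.96) = 0.716. If the two visits were independent, the pattern would have probability 0.716 × (1 − 0.716) = 0.203. Positive correlation lowers this. The simulated values are 17.8%, 14.7% and 11.4% at ρ = 0.3, 0.5 and 0.7, as expected.

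**3. Precision of the right contrasts**, in SD units, assuming 20 per cell:

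- Age-by-arm difference at one visit, unadjusted: SE = √(4/20) = 0.447.
- Adjusted for baseline at ρ = 0.5: 0.447 × √(1 − 0.25) = 0.387.
- Overall exercise-minus-control effect (40 v 40): SE = √(2/40) = 0.224, or 0.224 × √(1 − 0.25) = 0.194 adjusted.
- Smallest age-by-arm difference in change detectable with 80% power: (1.96 + 0.84) × √(2(1 − ρ)) × √(4/20) = 1.48, 1.25 and 0.97 SD at ρ = 0.3, 0.5 and 0.7.

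**The case against.** The strongest reply has four parts.

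- **No such decision rule exists.** A reader might infer from the title and the visit-by-visit tests that rejuvenation will be declared when an age gap is significant at baseline and not at Visit 4. The Protocol never says so; it gives tests and an alpha level, and no criterion for rejuvenation. This stands. The percentages describe what would happen if the tests were read that way; they are not an error rate of the plan.
- **A change analysis is stated.** The repeated-measures ANOVA works within individuals and so removes the baseline gap. Improvement in older exercisers could be read from it without comparing p-values across visits. This also stands, but as described it brings in neither the control group nor age.
- **A SAP may name the model terms.** The factors in a repeated-measures ANOVA are often left to a SAP, and nothing in the wording rules out age or arm as between-subject factors. That is fair for the second analysis. It does not cover the lead analysis, whose one-factor contrast the Protocol fixes itself.
- **The hypothesis is improvement in both ages, not narrowing of the gap.** This is right, and it sets the order of priority: the exercise-versus-control contrast comes first, and the age contrast is needed only for a claim about the age gap.

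The illustration is also sensitive to its inputs. At 40 per age group and a gap of 0.8 SD the chance pattern is about 4%, and at 1.0 SD it is below 1%. The 40 v 40 case pools the arms, so it is not an exercise comparison.

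**Conclusion.** The point holds in a limited form. The lead analysis cannot separate a response to exercise from an age gap already present at Visit 2, and the alternative names neither age nor arm. As written, no stated test estimates the exercise effect against the randomised control, and none tests whether that effect differs by age. This conclusion follows from the wording and the algebra alone.

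The size is conditional. It applies only if narrowing were inferred from lost significance, and it rests on assumed group sizes, gaps and correlations: with a constant gap, roughly 7-21% at 20 v 20 and 1-19% at 40 v 40, against 5% for a direct contrast. The documents do not support saying that the plan will draw its conclusion this way, or that it contains no analysis of change. The analysis wording should be corrected before the data are analysed; the design itself need not change.

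**What to change.** Make the main analysis a single model using data already collected: either post-baseline function adjusted for the Visit 2 value, or a longitudinal model over the three visits, with arm, age group, visit and their interactions. Then:

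1. Report first the exercise-minus-control effect on post-baseline function, overall and within each age group, with 95% CIs.
2. Report next the age-by-arm difference with its 95% CI, as the only basis for any claim that exercise changes the age gap.
3. Keep the Visit 2 age comparison as a descriptive baseline result.
4. State that a change in significance between visits will not be read as a narrowing of the gap.

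The cost is mainly wording; no extra visits, biopsies or participants are needed. The age groups must be defined before analysis. The team should confirm that the software named in the Protocol can fit the chosen model, or name one that can. The real downside is precision: with an assumed 20 per cell the age-by-arm SE is about 0.39-0.45 SD, giving a 95% CI of roughly ±0.76 to ±0.88 SD (1.96 × 0.387 and 1.96 × 0.447). Smaller or unequal cells would widen it. Any age claim becomes more modest.

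### For the randomised exercise-versus-control comparison, the plan names no analysis that adjusts for the pre-randomisation Visit 2 biopsy, although adjustment is at least as precise as either stated method

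*Protocol*

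**What the plan says.** Under Design and Procedures in the protocol, every participant has a muscle biopsy at Visit 2, and further biopsies follow at Visits 3 and 4 in both groups. Allocation comes after the first of these: "After Visit 2, subjects will be randomized to one of two intervention groups", one exercising and the other serving as sedentary controls. The Visit 2 value is therefore a true pre-randomisation baseline. The ceiling on numbers is in the same section: "Up to 80 adults, 21 years of age and greater, will undergo a consent visit".

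The section Data Analysis and Statistical Considerations names two methods. The first is: "Muscle stem cell function will be compared across age groups at each time point using a One Way ANOVA or t test". The second is introduced with "An alternative analysis will be a longitudinal design following muscle stem cell function from each individual before and after exercise training", and the text adds "This analysis will be performed with repeated measure ANOVAs". The section also fixes the software and the significance level. It names no covariate and no exercise-versus-control comparison.

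The hypothesis, under Background and Significance, is that exercise improves muscle stem cell function in both young and older individuals.

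**The concern.** The hypothesis is about what exercise does, and the design randomises exercise. The comparison that answers it is exercise versus control at Visit 3 and at Visit 4, overall and within age group. If the methods in the analysis section are carried over to that comparison, neither uses the Visit 2 biopsy to best effect. A test on the follow-up value alone leaves all between-person variation in the error term. A repeated-measures ANOVA treats baseline as one more response. If arm is a factor, its baseline-to-follow-up contrast amounts to comparing changes, which is noisier than ignoring baseline when the correlation between visits is low.

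At most 80 people take part, divided by arm and again by age, and each has three biopsies. Any avoidable loss of precision is costly here. A chance imbalance at baseline in groups this small would also go uncorrected in a follow-up-only test.

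**Working it through.** The protocol states no power, effect size, standard deviation or correlation, so there is no figure of its own to reproduce. What follows is an illustration over a range.

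**Inputs from the protocol:** at most 80 participants, two randomised groups, biopsies at Visits 2, 3 and 4, randomisation after Visit 2, significance at 0.05.

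**Assumptions:** all 80 enrol and contribute biopsies; 1:1 allocation (40 v 40); two age groups of equal size (20 v 20 within each); two-sided testing; the same SD at each visit; rho, the correlation between the Visit 2 value and the follow-up value within arm and age group, anywhere from 0 to 0.7.

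**Variance of an arm contrast at one follow-up visit, relative to a follow-up-only test:**

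- follow-up only: 1
- change from Visit 2: 1 + 1 − 2·rho = 2(1 − rho)
- analysis of covariance on Visit 2: 1 − rho²

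Two facts follow. First, 1 − rho² never exceeds 1. Second, 2(1 − rho) − (1 − rho²) = (1 − rho)², which is never negative. Adjustment is thus at least as precise as both alternatives, apart from the one degree of freedom spent on the covariate. The change score is worse than follow-up only whenever 2(1 − rho) > 1, that is, when rho < 0.5.

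| rho | follow-up only | change | adjusted |
|---|---|---|---|
| 0 | 1.00 | 2.00 | 1.00 |
| 0.3 | 1.00 | 1.40 | 0.91 |
| 0.5 | 1.00 | 1.00 | 0.75 |
| 0.7 | 1.00 | 0.60 | 0.51 |

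**Power for a difference of 0.6 SD** (an illustrative effect; noncentral t with noncentrality 0.6·√(n/2)/√v, where n is the number per arm and v is the relative variance above):

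| rho | 40 v 40: follow-up only | 40 v 40: change | 40 v 40: adjusted | 20 v 20: follow-up only | 20 v 20: adjusted |
|---|---|---|---|---|---|
| 0 | 75.5% | 46.6% | 75.5% | 45.6% | 45.5% |
| 0.3 | 75.5% | 61.0% | 79.3% | 45.6% | 49.1% |
| 0.5 | 75.5% | 75.5% | 86.4% | 45.6% | 56.9% |
| 0.7 | 75.5% | 92.8% | 96.0% | 45.6% | 73.5% |

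**Difference detectable with 80% power, 40 v 40:** 0.634 SD from follow-up alone; 0.605, 0.549 and 0.453 SD after adjustment at rho 0.3, 0.5 and 0.7. With 20 v 20 the values are 0.909 SD, against 0.868, 0.788 and 0.650 SD.

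**Equivalent sample size:** to match the adjusted analysis of 80 people, a follow-up-only test would need 80/(1 − rho²) participants: 80/0.91 ≈ 88, 80/0.75 ≈ 107 and 80/0.51 ≈ 157.

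**The case against.** Several points on the other side stand.

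- **Baseline is not ignored altogether.** A reader might infer that no stated analysis uses Visit 2. The text does not support that: the repeated-measures option follows each person from before training, uses the Visit 2 value and removes stable between-person differences. Its weakness is narrower. If arm is in the model, its baseline-to-follow-up contrast is a change score. The text does not mention an arm factor; for a purely within-person before-and-after comparison, baseline is the comparator and the question of a covariate does not arise.
- **The per-visit tests named are between age groups.** A reader might infer that these tests lose precision for no reason. They do not. Age is not randomised, and adjusting a young-versus-old comparison for baseline changes the question to the follow-up difference between people who started level. The argument applies only to the randomised contrast, which the analysis section does not name.
- **The size is unknown.** With no correlation given, the gain cannot be fixed. At rho = 0 it is nil, and at 0.3 power moves only from 75.5% to 79.3%.
- **Covariates are often left to a statistical analysis plan**, which may exist. That would answer mere silence. This section goes further and names specific tests, and those tests are what the point addresses.
- **The stated methods are valid.** Nothing here shows bias; the issue is efficiency.

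**Conclusion.** The point holds for the exercise-versus-control contrast and only for that. The hypothesis needs this contrast, a pre-randomisation value is scheduled for everyone, and baseline adjustment is never less precise than a follow-up-only or change-score comparison, apart from one degree of freedom. The benefit ranges from nothing at rho = 0 to roughly halving the variance (0.51) at rho = 0.7. The algebra assumes equal SDs across visits; the power figures also assume full enrolment, 1:1 allocation and two equal age groups. The change-score criticism of the repeated-measures option depends on arm being included in it. This is a worthwhile, low-cost improvement in precision and not a defect in validity.

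**What to change.** State that the exercise-versus-control comparison at Visit 3, and separately at Visit 4, is an analysis of covariance of that visit's value, with arm, age group and the arm-by-age interaction as factors and the Visit 2 value as covariate. Report the adjusted arm contrast overall and within each age group, with confidence intervals. The interaction term is needed because without it the model gives no age-specific arm effects.

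Keep the young-versus-old comparison at each time point as a separate descriptive analysis, not adjusted for baseline, because age is not randomised.

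The cost is a few lines of analysis text, one degree of freedom for the covariate and a little more analysis work, including a check that the named software can fit the model. No additional biopsies, visits or participants are required.

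### If the repeated-measures ANOVA is run as one classical model over all three biopsy visits, leaving before Visit 4 also removes a participant from the Visit 2 to Visit 3 acute contrast

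*Protocol*

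**What the plan says.** DESIGN AND PROCEDURES sets three blood and biopsy visits: "baseline (pre), after the first exercise bout (post-acute), and after the 12 week training program (post-chronic"). It allows for "Up to 80 adults, 21 years of age and greater, will undergo a consent visit". Allocation comes after the first biopsy: "After Visit 2, subjects will be randomized to one of two intervention groups". In the exercise arm, Visit 3 is close to the start of training: "this will take place approximately 2-hours after the first bout of exercise". Visit 4 follows the last session of a 10–12 week programme; in controls it falls 10–12 weeks after Visit 3.

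DATA ANALYSIS AND STATISTICAL CONSIDERATIONS lists two analyses. The first is between age groups, visit by visit: "Muscle stem cell function will be compared across age groups at each time point using a One Way ANOVA or t test for specific comparisons". The second is within person: "An alternative analysis will be a longitudinal design following muscle stem cell function from each individual before and after exercise training". Its method is one sentence: "This analysis will be performed with repeated measure ANOVAs". The section does not say which visits enter each ANOVA or what happens to a participant with a visit missing.

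**The concern.** A classical repeated-measures ANOVA with visit at three levels needs all three values from each person. The acute response is fully measured by Visit 3, before the 10–12 weeks in which people are most likely to leave. In a three-visit complete-case model, whether someone attends Visit 4 decides whether their acute response counts.

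Two things are at stake. One is precision, in a study of at most 80 people whose samples are obtained by biopsy. The other is possible bias in the acute result, if leaving is related to how a person responded. Loss could plausibly differ by arm: exercisers must attend three supervised sessions a week and face the soreness and injury risks that the protocol lists, while controls are asked only to stay inactive.

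**Working it through.** The protocol gives no power calculation, SD, drop-out rate or allocation ratio, so there is no planned figure to reproduce. What follows is an illustration.

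**Inputs from the protocol.** At most 80 participants, two arms, three biopsy visits, significance at 0.05.

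**Assumed inputs.** 1:1 allocation (40 per arm); 20% of exercisers and 5% of controls lost after Visit 3; unit SD at each visit; the same correlation r between any two visits, 0.4 or 0.6; two-sided testing.

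**1. Who is removed.** Exercisers lost: 40 × 0.20 = 8, leaving 32. Controls lost: 40 × 0.05 = 2, leaving 38. Ten people, with 10 × 2 = 20 biopsies from Visits 2 and 3, leave the three-visit model.

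**2. Precision of the acute between-arm contrast.** The SD of the change cancels, so the ratio of standard errors is

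sqrt(1/32 + 1/38) / sqrt(1/40 + 1/40) = 0.2399 / 0.2236 = 1.073, about 7% larger than needed.

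**3. Range over equal loss d in both arms.** Completers = 80(1 − d); Visit 2 and 3 biopsies unused = 160d; standard error ratio = sqrt(1/(1 − d)). Power is for an acute between-arm effect set to give 80% with all 80 (0.63 SD of the change).

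| Loss d | Completers | Biopsies unused (of 160) | SE ratio | Power |
|---|---|---|---|---|
| 5% | 76 | 8 | 1.03 | not computed |
| 10% | 72 | 16 | 1.05 | 76% |
| 20% | 64 | 32 | 1.12 | 71% |
| 30% | 56 | 48 | 1.20 | 65% |

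**4. Does the choice of visits matter?** In simulated data with 16 of 80 lacking Visit 4, the classical three-visit ANOVA could not be fitted until those 16 were dropped, leaving 64. A repeated-measures ANOVA on Visits 2 and 3 alone used all 80 (79 denominator degrees of freedom). A mixed model fitted to all three visits took every available sample.

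**5. Bias if drop-out depends on the Visit 3 value.** Let drop-out be logistic in the Visit 3 value, with lower values more likely to leave and a slope of 0.7 or 1.0 per SD. Let m be the resulting upward shift in mean Visit 3 value among those retained. By simulation, m is 0.129 or 0.172 SD at 20% loss, and 0.033 or 0.046 SD at 5% loss. With equal correlations, the Visit 2 and Visit 4 means each shift by r × m. Hence:

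- Acute change within the exercise arm: (1 − r)m. Lowest: 0.4 × 0.129 = 0.052. Highest: 0.6 × 0.172 = 0.103. A separate simulation with loss of about 20% gave 0.053–0.106, so the range is about 0.05–0.11 SD.
- Acute change between arms: (1 − r)(m exercise − m control). Lowest: 0.4 × (0.129 − 0.033) = 0.038. Highest: 0.6 × (0.172 − 0.046) = 0.076. The range is about 0.04–0.08 SD.
- Visit 4 minus Visit 2: r × m − r × m = 0.

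For scale, the standard error of the between-arm acute contrast among completers is sqrt(2(1 − r)) × 0.2399, which is 0.26 SD at r = 0.4 and 0.21 SD at r = 0.6. The largest between-arm bias is 0.076 / 0.263 = 0.29 of a standard error.

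**The case against.** **The three-visit model is an inference.** A reader might take the protocol to specify one ANOVA over three visits. It does not. It speaks of before and after training, and of ANOVAs in the plural. Separate two-visit comparisons fit that wording, and a Visit 2 versus Visit 3 ANOVA loses nobody who has those two samples. This stands, so the point has to be conditional. The text still leaves both readings open, and they analyse different sets of people.

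**It is the alternative analysis.** A reader might infer that leavers' biopsies are lost to the study and that every acute result becomes a completers-only result. Neither follows, because the first-listed comparison uses whatever samples exist at each visit. But that comparison is between age groups and estimates nobody's change. The hypothesis that exercise raises stem cell function in young and older people concerns change, and repeated-measures ANOVA is the only within-person method named.

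**The training contrast is not biased.** Before and after training most naturally means Visit 2 to Visit 4, which is unbiased in the model above. This stands, although it depends on the equal correlations assumed there.

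**Missing-data detail belongs in the SAP.** An SAP may exist that is not shown, so the lack of a missing-data rule is no finding. The point concerns the method the protocol does name, and how well it suits this visit schedule.

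**The size is assumed and modest.** This also stands. Every drop-out input is an assumption, and nothing in the protocol shows that people leave according to a muscle-cell measurement.

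**Conclusion.** The point holds conditionally and is minor to moderate. The structural part needs no assumption about drop-out rates: a classical three-visit ANOVA makes the acute contrast depend on attending Visit 4, and the protocol does not rule that model out.

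The size does depend on assumptions. The precision loss is about 7% in the standard error under the 20%/5% split, and 3–20% over 5–30% equal loss. The bias arises only if drop-out is related to response, and between arms it stays under one third of a standard error in the scenarios tried. The documents do not support saying that the trial will lose these biopsies, or that its training effect is biased. The matter is worth changing because a better method is available at little cost, not because the planned analysis is invalid.

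**What to change.** Replace the repeated-measures ANOVA with a linear mixed model: visit as a category, arm, age group and their interactions, with within-person correlation modelled. Fit it to every available sample from everyone randomised, and take the Visit 3 and Visit 4 contrasts from that one model. Keep the complete-case ANOVA as a sensitivity analysis. If drop-out depends only on values already observed, as in the scenario above, an adequately specified likelihood-based fit also removes the acute bias.

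At minimum, state which visits enter each ANOVA and run Visit 2 versus Visit 3 separately, so that the acute result does not depend on attending Visit 4.

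The cost is a sentence or two of analysis text, software that fits mixed models, and slightly more analysis work. No new data or visits are needed.
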